8.2.9 Availability & Supply

The supply for this study will be investigational – not commercially available. Supply will be provided by BMS free of charge. Nivolumab will be supplied as 100 mg/vial (10mg/mL). Drug is protocol specific, but not patient specific.

A supply of nivolumab may be ordered from by completing a Drug Request Form provided by BMS. The first request may take place upon screening of the first patient. The initial order should be limited to 20 vials. Allow 5 business days for shipment of drug from BMS receipt of the Drug Request Form. Drug is protocol specific, but not patient specific. All drug product will be shipped by courier in a temperature-controlled container. It is imperative that only drug product designated for this protocol number be used for this study.

Drug re-supply request form should be submitted electronically 10 business days before the expected delivery date. Deliveries will be made Tuesday through Friday.

When assessing need for resupply, keep in mind the number of vials used per treatment dose, and that shipments may take 14 business days from receipt of request. Drug is not patient-specific.

8.2.10 Side effects

Below are safety data from 268 subjects with unresectable or metastatic melanoma and 117 patients with metastatic squamous NSCLC who received nivolumab alone. Related side effects reported in subjects receiving nivolumab alone were:

Very Frequent – Expected to occur in more than 20% of people (more than 20 out of 100 people): Fatigue (50%), Dyspnea (38%), Musculoskeletal pain (36%), Rash (21%), Increased AST (28%), Increase alkaline phosphatase (22%), Hyponatremia (25-38%)

Frequent - Expected to occur in 10% to 20% of people (10 to 20 out of 100 people): Pruritus (19%), Cough (17%), URI (11%), Peripheral edema (10%), Increased ALT (16%), Hyperkalemia (15%)

NU Study Number: NU 16101
BMS Study Number: CA 209-615

Not Frequent – Expected to occur in less than 10% of people (less than 10 out of 100 people): ventricular arrhythmia, iridocyclitis, infusion-related reactions, increased amylase, increased lipase, dizziness, peripheral and sensory neuropathy, exfoliative dermatitis, erythema multiforme, vitiligo, psoriasis

Deaths thought to be related to nivolumab when given alone were reported in approximately 0.5% of subjects treated (approximately 1 out 200 people).

For the most recent safety update, please refer to the current Investigator’s Brochure or Study Agent Prescribing Information.

8.2.11 Return and Retention of Study Drug

The clinical study team will be responsible for keeping accurate records of the clinical supplies received from BMS or designee, the amount dispensed to and returned by the subjects and the amount remaining at the conclusion of the trial.

Upon completion or termination of the study, all unused and/or partially used investigational product will be destroyed at the site per institutional policy. It is the Investigator’s responsibility to arrange for disposal of all empty containers, provided that procedures for proper disposal have been established according to applicable federal, state, local and institutional guidelines and procedures, and provided that appropriate records of disposal are kept.

Table 8.1 – Nivolumab Product Information				
Product Description and Dosage Form	Potency	Primary Packaging (Volume)/ Label Type	Appearance	Storage Conditions (per label)
Nivolumab BMS-936558-01 Solution for Injection ^a	100 mg (10 mg/vial)	10 mL vial	Clear to opalescent colorless to pale yellow liquid. May contain particles	2 to 8°C. Protect from light and freezing

9.0 CORRELATIVES/SPECIAL STUDIES

The goal of the planned laboratory correlative studies is to identify biomarkers that help predict benefit and/or toxicities from the study drug. A separate Laboratory Manual will be developed and maintained with detailed sample collection and procurement guidelines, processing instructions, and additional assay descriptions. The Laboratory Manual will also include all contact information for key personnel and departments involved with correlative studies for this protocol.

9.1 Sample Collection Guidelines

Peripheral blood samples will be collected for all patients pre-dose on Cycle 1 Day 1 as well as every 8 weeks for the first 24 weeks, and every 16 weeks thereafter.

If patient has archival tissue available, it will be collected for next-generation sequencing (NGS) and immunohistochemistry (IHC). See lab manual for collection details.

9.2 Sample Processing, Storage, and Shipment

All samples will be processed by PCF-CTU according to instructions in the lab manual. Samples will be labeled with the subject’s de-identified study number and collection date.

9.3 Assay Methodology

9.3.1 Tumor biopsy immunohistochemical (IHC) staining and analysis for PD-L1, PD-1, CD8+ and CD4+ tumor infiltrating lymphocytes

Detection of the selected markers for this study will be performed using immunohistochemistry. After the staining, the slides will be digitally scanned in an Aperio AT system (Aperio™, Leica Biosystems™) to convert the IHC slides into digital pathology files for posterior analysis. IHC expression analyses of markers consider a thorough staining pattern evaluation including distribution (percentage of positive cells) and intensity in the form of H-score, and evaluating the IHC expression in the proper subcellular location (i.e. membrane, cytoplasm or nucleus). IHC analysis and scoring will be performed by a certified pathologist using an image analysis software (Image Toolbox, Aperio™).

Outcome from the analysis will be calculated according to the H-score. The H-score ranges from 0 to 300, and it considers both intensity of the IHC (from 0 to 3) and distribution (percentage of the target cells positive, from 0 to 100). The scoring is the addition of the percentages of cells with intensity 0 + intensity 2 + intensity 3, thus the addition of the final percentage is 100% and the scoring will range from 0 to 300. Hence, the H score will incorporate both percentage of positive cells and intensity of marker expression. Hematoxylin/eosin and PD-1, PD-L1 and PD-L2-stained sections will be reviewed by a pathologist. Criteria to be evaluated include histologic subtype and grade, TNM 2002 pathologic tumor stage, the presence and type of intratumoral lymphocytic infiltration, and the quantity and location of PD-L1 staining. The tumor will be considered positive for PD-1, PD- L1, PD-L2 if >5% of tumor cells had histologic evidence of plasma membrane staining.

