1.5 Exploratory Studies

It has been shown in animal models, control human subjects as well as in oncology patients that, administration of nivolumab modifies the cytokine levels in plasma.

1.5.1 Exploration of the correlation between PD-1, PD-L1 and PD-L2 expression and CD4+ and CD8+ tumor infiltrating lymphocytes and PFS, OS and response to treatment.

PD-1 is a key immune checkpoint receptor expressed by activated T cells and mediates immunosuppression. PD-1 functions primarily in peripheral tissues, where T cells may encounter the immunosuppressive PD-1 ligands PD-L1 and PDL-2, which are expressed by tumor cells, stromal cells or both [1-3]. PD-L1 and PD-L2 are overexpressed in a variety of solid tumors however no data exists in ACC [1].

There are conflicting data on the predictive value of PD-L1 expression on PD-1 directed therapy in solid tumors [1, 4]. Herbst et al showed that patients with solid tumors including non-small cell lung cancer and melanoma treated with humanized PD-L1 antibody had higher ORR when immunohistochemistry showed intense staining for PD-L1 in the tumor [5]. The same correlation was not observed on stratified analysis according to tumor cell membrane PD-L1 expression of non-small cell lung cancer patients treated with nivolumab therapy in the second line setting [4].

Pathological slides from tumor archival tissue will be stained using a monoclonal antibody against PD-L1 and defined as PD-L1 positive if equal or greater than 5% of the tumor cells membrane analyzed. We hypothesize that tumor cell membrane expression of PD-L1 or PD-L2 can have an impact on treatment responses.

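### The H-score sentence in section 9.3.1 is wrong as written and contradicts the 0 to 300 range in its own paragraph; the PD-L1 cut-off also differs between sections 1.5.1 and 9.3.1

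*Combined protocol and SAP*

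**What the plan says.** Section 9.3.1 makes the H-score the outcome of the immunohistochemistry analysis and describes it in four statements.

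- Range and components: "The H-score ranges from 0 to 300, and it considers both intensity of the IHC (from 0 to 3) and distribution", where distribution is the percentage of target cells that stain, from 0 to 100.
- Rule: "The scoring is the addition of the percentages of cells with intensity 0 + intensity 2 + intensity 3".
- Continuation of that sentence: "thus the addition of the final percentage is 100% and the scoring will range from 0 to 300".
- Purpose: "the H score will incorporate both percentage of positive cells and intensity of marker expression".

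The same section sets a separate yes/no rule for PD-1, PD-L1 and PD-L2. A tumour is positive "if >5% of tumor cells had histologic evidence of plasma membrane staining". Section 1.5.1 also gives a rule for PD-L1: archival slides are "defined as PD-L1 positive if equal or greater than 5" per cent of tumour cell membranes.

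On who scores, section 9.3.1 says "IHC analysis and scoring will be performed by a certified pathologist using an image analysis software". Section 9.0 refers to a separate Laboratory Manual with "processing instructions, and additional assay descriptions". That manual is not among the documents.

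**The concern.** The rule sentence is the only H-score formula in the documents, and it does not fit the statements on either side of it. It counts cells that do not stain, drops cells that stain weakly, and gives a moderately stained cell the same credit as a strongly stained one. A sum of percentages taken from one set of cells cannot exceed 100, so a range up to 300 is out of reach.

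At stake is the exploratory biomarker work. Section 1.5.1 plans to relate PD-1, PD-L1 and PD-L2 expression to response, PFS and OS, and section 2.3.1 makes marker expression an exploratory objective. If anyone computed the score from the sentence as printed, negative tumours would rank above weakly stained ones and level with strongly stained ones. Section 11.8 requires the study to be run as the approved protocol describes, so the printed rule should be one that can be followed.

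The two PD-L1 cut-offs raise a smaller, separate question: the status of a tumour at exactly 5% depends on which section is read.

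**Working it through.** **Inputs.** Let P0, P1, P2 and P3 be the percentages of target cells at intensity 0, 1, 2 and 3. The intensity scale (0 to 3), the percentage scale (0 to 100) and the stated range (0 to 300) all come from section 9.3.1. Every cell falls in one class, so P0 + P1 + P2 + P3 = 100.

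**Reproducing the plan's figure.** A maximum of 300 needs the intensity to act as a multiplier: 3 x 100 = 300 when every cell is at intensity 3. The minimum of 0 then occurs when every cell is at intensity 0.

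**The printed rule.** P0 + P2 + P3 = 100 - P1. The literal score is therefore 100 minus the weakly stained percentage. It runs from 0 to 100 and carries no information on how the remaining cells divide among negative, moderate and strong.

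**Five readings compared.** The last column is a tumour with 60/20/15/5% of cells at intensity 0/1/2/3, chosen for illustration.

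| Reading | Range | All 0 | All 1 | All 2 | All 3 | Example |
|---|---|---|---|---|---|---|
| (a) Literal: P0 + P2 + P3 | 0 to 100 | 100 | 0 | 100 | 100 | 80 |
| (b) 0 taken as a misprint for 1, no weights: P1 + P2 + P3 | 0 to 100 | 0 | 100 | 100 | 100 | 40 |
| (c) All four classes, no weights | always 100 | 100 | 100 | 100 | 100 | 100 |
| (d) Listed intensities used as weights: 0 x P0 + 2 x P2 + 3 x P3 | 0 to 300 | 0 | 0 | 200 | 300 | 45 |
| (e) All intensities used as weights: 1 x P1 + 2 x P2 + 3 x P3 | 0 to 300 | 0 | 100 | 200 | 300 | 65 |

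For the example, (a) is 60 + 15 + 5 = 80, (d) is 2 x 15 + 3 x 5 = 45, and (e) is 20 + 2 x 15 + 3 x 5 = 65.

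**Choosing among them.** The stated range rules out (a), (b) and (c). Between (d) and (e), the sentence says the percentages total 100%. The three classes it lists total 100% only when P1 = 0, so intensity 1 has to be included in general. Reading (d) also scores weak staining the same as none, which does not fit a score meant to reflect the percentage of positive cells. Only (e) gives 0 to 300 and covers every class. Two repairs are needed to reach it from the printed sentence: the missing class and the missing weights. Correcting 0 to 1 alone leads to (b), which still stops at 100.

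**The cut-offs.** At exactly 5% staining, the rule in section 1.5.1 (5 or more) gives PD-L1 positive and the rule in section 9.3.1 (more than 5) gives negative. At every other value the two numerical thresholds agree. The documents do not allow an estimate of how many tumours would be scored at exactly 5%.

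**The case against.** The strongest reply is that this is a drafting slip whose meaning can be recovered on the spot. The paragraph gives the range twice, names an intensity scale of 0 to 3 and says the score combines intensity with percentage. A certified pathologist with image-analysis software does the scoring, and the Laboratory Manual may hold the correct formula. The figures of 100 for an all-negative and 100 for an all-strong tumour also depend on the unweighted reading; under reading (d) they become 0 and 300.

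Much of this stands. A reader might infer that the plan's biomarker analysis is wrong, or that any correlation of PD-1, PD-L1 or PD-L2 with outcome would be biased or meaningless. The documents do not support that. Nothing in them shows that the literal sum would be computed. Positivity for the three markers rests on the percentage of tumour cells with membrane staining, not on the H-score, so an analysis by positive or negative status does not depend on this sentence. Section 10.2 names no H-score analysis.

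The reply does not rescue the sentence itself. It is current text, it cannot produce the range printed beside it, and the reader has to rebuild the rule. The difference in cut-offs is not answered by any of these arguments.

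**Conclusion.** The sentence in section 9.3.1 is wrong as written. Taken literally it spans 0 to 100 instead of 0 to 300, ranks an all-negative tumour (100) above an all-weak one (0), and cannot separate all-negative, all-moderate and all-strong tumours (100 each). These figures assume literal, unweighted use. Whether anyone would score that way cannot be settled without the Laboratory Manual and the software settings.

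The possible harm is confined to an exploratory correlation based on a literally computed H-score. MTD, ORR, the two-stage Simon design and the sample size do not use the score. The two PD-L1 cut-offs conflict only at exactly 5%. Overall the point is minor, but it should be corrected.

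**What to change.** In section 9.3.1, replace the rule sentence with: H-score = 1 x (% of cells at intensity 1) + 2 x (% at intensity 2) + 3 x (% at intensity 3), range 0 to 300, with the percentages over intensities 0 to 3 totalling 100%. Confirm that the Laboratory Manual and the image-analysis settings use the same formula. If slides have already been scored, check which rule was applied.

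Choose one positivity cut-off, either 5% or more or above 5%, and state it identically in sections 1.5.1 and 9.3.1.

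The cost is wording in the protocol and, if needed, the Laboratory Manual. No new samples or assays are required.

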1.2 Intervention Background & Overview

1.2.1 Preclinical Evidence for the PD-1 pathway in HCC:

The role of immune surveillance in controlling growth and the oncogenic properties have been well established for several decades. There is now a plethora of evidence that describes the correlation between tumor-infiltrating lymphocytes (TILs) within tumor cells and favorable prognosis overall.

The PD-1 pathway is a major component of tumorigenesis by suppressing the immune system. The innate function of the PD-1, when expressed on activated T-cells is to down regulate unwanted / excessive immune responses thus controlling autoimmune conditions.

PD-1 is a T-cell co-inhibitory receptor with two well-recognized ligand PD-L1 (B7-H1) and PD-L2 (B7-DC)¹². The binding of PD-1 to PD-L1 leads to T-cell activation and ultimately several immunosuppressive effects, which includes inhibition of cell survival factor Bcl-xL^(13,14). Within the HCC, a significant proportion of PD-L1 is expressed by Kupffer cells⁽¹⁵⁾ and in turn this expression is driven by IL-10 in HCC. The expression of PD-1 is markedly higher in the tumor and peripheral blood of patients with HCC compared to controls with cirrhosis alone (16).

A study of 54 patients with HCC and HBV co-infection who underwent surgical resection, the levels of Pd-1 expression was evaluated. This study demonstrated that higher versus lower expression of intrahepatic PD-1 on T-cells was associated with lower disease free survival (13.6 mths vs. 28.7 mths; $p < 0.001$) (17). Similar results were mirrored when the expression of PD-1 in peripheral blood was measured. In addition, the levels of circulating PD-1 correlated directly with the stage of HCC. This small study clearly demonstrated that higher levels of PD-1 expression in the tumor microenvironment are associated with worse overall survival & prognosis. (17)

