8.2.3 Mode of action

Nivolumab acts as an immunomodulator by blocking ligand activation of the programmed cell death 1 (PD-1) receptor on activated T cells anti-PD1.

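### Section 9.3.1 scores PD-1 positivity on tumor cells although the protocol describes PD-1 as a T-cell receptor, and the PD-L1 cut-off differs between sections 1.5.1 and 9.3.1

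*Combined protocol and SAP*

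**What the plan says.** Section 1.5.1 announces the exploratory analysis in its heading: "Exploration of the correlation between PD-1, PD-L1 and PD-L2 expression and CD4+ and CD8+ tumor infiltrating lymphocytes and PFS, OS and response to treatment". The text below it identifies the cells involved. Of the receptor it says "PD-1 is a key immune checkpoint receptor expressed by activated T cells and mediates immunosuppression". Of the other side of the pathway it speaks of "immunosuppressive PD-1 ligands PD-L1 and PDL-2, which are expressed by tumor cells, stromal cells or both". The section's hypothesis about tumor-cell membrane staining names PD-L1 and PD-L2, not PD-1. Its PD-L1 rule is "defined as PD-L1 positive if equal or greater than 5% of the tumor cells membrane analyzed".

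Sections 1.2.1 and 8.2.3 agree on the receptor: "PD-1 is a T-cell co-inhibitory receptor with two well-recognized ligand PD-L1 (B7-H1) and PD-L2 (B7-DC)" and "programmed cell death 1 (PD-1) receptor on activated T cells". The prognostic study summarized in 1.2.1 also concerns PD-1 on T cells within the liver. Objective 2.3.1 specifies tumor cells for PD-L1 and lists PD-1 among the inflammatory and immune markers.

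Section 9.3.1, the assay method, ends with a single rule for all three markers: "The tumor will be considered positive for PD-1, PD- L1, PD-L2 if >5% of tumor cells had histologic evidence of plasma membrane staining". The same section says that the outcome will be an H-score based on a share of target cells, without saying which cells these are for each marker. Section 10.2 does not say which measure is to be related to response.

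**The concern.** A biomarker correlation can only be as good as the classification that enters it. If the PD-1 rule looks at cells other than those on which the protocol places PD-1, the resulting groups do not separate patients by T-cell PD-1. An absent association would then say little about the hypothesis, and an observed one could be misread.

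The PD-L1 discrepancy is a different problem. The compartment is the intended one, but two current sections draw the line differently. If the choice between them is left until outcomes are known, it becomes a small analytic freedom that should not exist. Section 9.0 says that these studies aim to identify markers predicting benefit or toxicity, so positivity should be fixed in advance.

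**Working it through.** The plan gives no sample size, power or error rate for the biomarker correlation, so there is no stated figure to reproduce. The check is a comparison of texts, followed by a bound on the cut-off conflict.

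**1. Which cells are scored, and which cells does the protocol say carry the marker?**

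| Marker | Cells said to carry it | Cells scored in 9.3.1 | Match? |
|---|---|---|---|
| PD-1 | T cells (1.2.1); activated T cells (1.5.1, 8.2.3) | Tumor cells | No |
| PD-L1 | Tumor cells, stromal cells or both (1.5.1); objective 2.3.1 specifies tumor cells | Tumor cells | Yes, for the stated objective |
| PD-L2 | Tumor cells, stromal cells or both (1.5.1); hypothesis names tumor-cell membrane | Tumor cells | Yes, for the stated hypothesis |

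No section gives a reason for scoring PD-1 on tumor cells.

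**2. Consequence for PD-1.** The 9.3.1 rule is (tumor cells with membrane staining) / (tumor cells) > 5%. Lymphocytes enter neither numerator nor denominator. The share of PD-1-positive lymphocytes could be anywhere from 0% to 100% without changing the classification.

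**3. PD-L1 cut-off.** Let x be the percentage of tumor cells with membrane staining.

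| Reading | 1.5.1 (x ≥ 5%) | 9.3.1 (x > 5%) |
|---|---|---|
| x < 5% | negative | negative |
| x = 5% | positive | negative |
| x > 5% | positive | positive |

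The rules disagree only at exactly 5%.

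**4. How many patients could that be?** Inputs: n = 29, the evaluable Phase 1b patients in section 10.1, assuming tissue from all of them; and q, the share of samples read at exactly 5%. The documents do not give q, so a range of 2% to 10% is assumed. The expected number is n × q, and the chance of at least one is 1 − (1 − q)^n.

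- q = 2%: 29 × 0.02 = 0.58; 1 − 0.98^29 = 0.443
- q = 5%: 29 × 0.05 = 1.45; 1 − 0.95^29 = 0.774
- q = 10%: 29 × 0.10 = 2.90; 1 − 0.90^29 = 0.953

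Criterion 3.1.12 requires archived tissue only where enough exists, so the true n may be well below 29. With tissue from 10 patients (an assumption), the expected numbers are 0.2, 0.5 and 1.0, and the chances of at least one are 0.183, 0.401 and 0.651.

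**5. Does the H-score settle the PD-1 question?** As printed, it adds the percentages of cells at intensities 0, 2 and 3. That sum omits intensity 1 and has no weights, so it runs from 0 to 100. The stated range of 0 to 300 needs 1 × (percent at 1) + 2 × (percent at 2) + 3 × (percent at 3). A weighted score was evidently meant, but the cell population for PD-1 is still not named.

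**The case against.** The strongest reply is that 9.3.1 names the H-score as its outcome, that its target cells need not be tumor cells, and that nothing says the 5% grouping enters the correlation. This stands in part. A reader might infer from the PD-1 rule that no correlation could be computed at all. The documents do not support that, because a continuous score is also planned. The H-score does not repair the rule, however: its target cells are undefined for each marker and its printed formula cannot give its stated range. The instruction to read the proper subcellular location does not help either, since it distinguishes membrane, cytoplasm and nucleus, not cell types.

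A second reply is that T-cell PD-1 may be captured elsewhere. Objective 2.3.1 allows flow cytometry, 9.3.1 has the pathologist review lymphocytic infiltration, and 9.0 refers further assay detail to a Laboratory Manual that is not part of these documents. This is fair, and it means that the information need not be lost. But recording infiltration does not record PD-1 on those lymphocytes, and a manual that said something else would conflict with an explicit protocol rule.

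A reader might also extend the compartment criticism to PD-L1, because section 1.2.1 says that "a significant proportion of PD-L1 is expressed by Kupffer cells". That does not hold. Tumor-cell scoring of PD-L1 matches objective 2.3.1 and the hypothesis in 1.5.1, and 9.3.1 already asks the pathologist to assess how much PD-L1 staining there is and where it lies.

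Finally, the analysis is exploratory, with no decision rule attached. That is correct and limits the weight of the point.

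**Conclusion.** The point holds in two limited parts. First, the stated PD-1 rule scores a different cell type from the one on which the protocol places PD-1, and would call a lymphocyte-rich, PD-1-expressing tumor negative. This follows from the text and needs no numerical assumption. It is tempting to add that nearly every patient would be PD-1 negative, but the documents give no frequency of PD-1 on tumor cells, so the size of the negative group cannot be stated.

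Second, PD-L1 has two cut-offs in current text. They differ only at a reading of exactly 5%. The figure of about 0.6 to 2.9 of 29 patients rests on the assumed 2% to 10% share and on tissue from everyone; the real number is unknown and likely to be small.

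The MTD, the objective response rate and the Simon design use none of these markers and are unaffected. This is worth correcting in the exploratory plan, but it is no threat to the primary conclusions.

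**What to change.** - **Section 9.3.1, last sentence:** take PD-1 out of the tumor-cell rule and score it as the percentage of tumor-infiltrating lymphocytes that are PD-1 positive, on the same slides.
- **Sections 1.5.1 and 9.3.1:** keep PD-L1 and PD-L2 on tumor-cell membrane, with one cut-off worded identically in both places (for example, 5% or more) and fixed before slides are read.
- **Section 10.2:** state whether the H-score or the positive/negative grouping enters the correlation. If it is the H-score, name the cells scored for each marker and correct the formula in 9.3.1.

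The cost is wording in three sections and one extra score-sheet entry for PD-1 on lymphocytes. No additional tissue or reader is needed. If some slides have already been read, PD-1 would have to be re-read on them; 9.3.1 provides for digital scans, so this should be possible without new sections.
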